7.6.2.2. Reporting Other Special Situations

All other special situation reports must be reported on the special situations report form and forwarded to Gilead DSPH within 24 hours of the investigator becoming aware of the situation. These reports must consist of situations that involve Tenofovir DF and/or Gilead concomitant medications, but do not apply to non-Gilead concomitant medications.

Special situations involving non-Gilead concomitant medications do not need to be reported on the special situations report form; however, for special situations that result in renal or bone AEs due to a non-Gilead concomitant medication, the AE should be reported on the AE form.

Any inappropriate use of concomitant medications prohibited by this protocol should not be reported as “misuse,” but may be more appropriately documented as a protocol deviation.

Refer to Section [7.3](#) and the CRF/eCRF completion guidelines for full instructions on the mechanism of special situations reporting.

All clinical sequelae in relation to these special situation reports will be reported as AEs or SAEs at the same time using the AE CRF/eCRF and/or the SAE report form. Details of the symptoms and signs, clinical management, and outcome will be reported, when available.

8. STATISTICAL CONSIDERATIONS

8.1. Analysis Objectives and Endpoints

8.1.1. Analysis Objectives

The primary objective of this study is:

- To characterize the long term (i.e., 96 weeks of follow up) bone safety profile of open-label Tenofovir DF treatment in CHB-infected adolescents. This includes prospectively evaluating and comparing the BMD change between CHB infected adolescents 12 to < 18 years of age treated with Tenofovir DF in European treatment centers who are assigned to one of two schedules for renal and bone laboratory monitoring and BMD measurement. The primary study endpoint will be the percent changes in BMD from Baseline through study Week 96.

The secondary objectives of this study are as follows:

- To document all SADRs and all renal- and bone-related AEs including renal and bone laboratory abnormalities, as applicable
- To determine the time to diagnosis of renal and bone AEs and document the resulting patient management and outcome(s)
- To assess the clinical management and outcomes of any renal- or bone related \geq Grade 3 laboratory markers and clinical SAEs
- To assess the efficacy and tolerability of Tenofovir DF 300mg once daily in adolescents aged 12 to <18 years with CHB infection
- To assess the use of oral vitamin D, calcium and phosphate supplementation and explore the association between supplement use and rates of bone and renal AEs
- To describe the demographic characteristics, the disease characteristics, of adolescents with CHB infection treated with Tenofovir DF
- To describe reasons for discontinuation of Tenofovir DF.

8.1.2. Primary Endpoint

The primary endpoint of this study is:

- The identification of bone AEs occurring in subjects taking Tenofovir DF between Baseline and Week 96 of treatment, including the identification of $\geq 4\%$ percent reduction in BMD within subjects and between monitoring groups from Baseline.

8.1.3. Secondary Endpoints

- Documentation of renal or bone AEs and outcomes among subjects receiving Tenofovir DF, including rates of medication withdrawal or drug discontinuation
- Subjects' cumulative exposure time on Tenofovir DF at the time renal or bone AEs are detected up to and including Week 96 or to study discontinuation (subjects without renal or bone AEs will contribute cumulative exposure time on Tenofovir DF from Baseline to Week 96 or to study discontinuation). The cumulative time to renal or bone AEs will be expressed as incident rates.
- Documentation of the medical management and classification of detected renal or bone laboratory abnormalities
- Analysis of subjects' virological and immunological status from Baseline to Week 96 under real world treatment practices
- Report provider recommendations and subject adherence to dietary supplements (e.g., Vitamin D, calcium)
- Documentation of subject demographics, new medical issues, medications, biometrics, treatment adherence
- Reasons for discontinuation of Tenofovir DF

8.1.4. Other Endpoints of Interest

Not applicable

8.2. Analysis Conventions

All individual subject data will be listed as measured. All statistical summaries and analyses will be performed using SAS[®] software (SAS Institute, Cary, North Carolina, USA) or other standard software tools including the STATA software (STATA Corp LP, College Station, TX, USA).

8.2.1. Analysis Sets

The analysis set will be the Full Analysis Set (FAS), which includes all subjects enrolled in the study.

8.2.1.1. Efficacy

An efficacy analysis will be conducted after the last assigned subject reaches Week 96. The analysis will evaluate the difference in the proportion of subjects (Group 1 and 2 data will be pooled, as subjects have exposure to a single mode of therapy) achieving a composite endpoint of HBV DNA < 400 copies/mL and ALT normal at Week 72, using a two-sided Fisher exact test with a non-completer equals failure approach.

The primary analysis set for safety analyses will include all randomized subjects who received at least one dose of Tenofovir DF. All data collected during the course of the study (on treatment and during the treatment-free follow up window) will be included in the safety summaries. Normalized bone biomarker ranges (i.e., calcium, phosphorus, vitamin D levels, PTH, osteocalcin, bone alkaline phosphatase, N and C telopeptides) in pediatric populations have not been established. Bone serum biomarkers will be collected in parallel to DEXA scan schedules for Groups 1 and 2 and summarized and compared to DEXA z-score findings.

8.2.1.2. Interim Analysis

An analysis for collected renal and bone adverse event data will be conducted after the first 50 patients are enrolled and complete Week 48 of the study. Final analyses will be conducted after all subjects have completed the study. All data collected during treatment plus 30 days will be included in the safety summaries.

8.2.1.3. Pharmacokinetics

Not applicable

8.2.1.4. Biomarkers

Not applicable

8.3. Data Handling Conventions

Missing data can have an impact upon the interpretation of the trial data. In general, values for missing data will not be imputed.

For the primary endpoint and categorical secondary efficacy endpoints, missing data will be detailed in a separate statistical analysis plan.

Sensitivity analyses will be performed if warranted.

8.4. Demographic Data and Baseline Characteristics

Demographic and baseline measurements will be summarized using standard descriptive methods

Demographic summaries will include sex, race/ethnicity, randomization stratification group, and age.

Baseline data will include a summary of body weight, height, body mass index, \log_{10} (HBV DNA) level, HBV serology, liver tests, creatinine clearance calculations using the Schwartz formula, hematology, previous nucleoside and interferon exposure, genotype, bone mineral density (via DEXA scan), and serum bone biochemical markers.

For categorical demographic and baseline characteristics, a two-sided Fisher exact test may be used to compare monitoring groups. Similarly, for continuous demographic and baseline characteristics, a Wilcoxon rank sum test may be used to compare monitoring groups.

8.5. Efficacy Analysis

8.5.1. Primary Analysis

An efficacy analysis will be conducted after the last assigned subject reaches Week 96. The analysis will evaluate the difference in the proportion of subjects (Group 1 and 2 data will be pooled, as subjects have exposure to a single mode of therapy) achieving a composite endpoint of HBV DNA < 400 copies/mL and ALT normal at Week 96, using a two-sided Fisher exact test with a non-completer equals failure approach.

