2. OBJECTIVES

The primary objective of this study is as follows:

- To characterize the long term (i.e., 96 weeks of follow up) bone safety profile of open-label Tenofovir DF treatment in CHB-infected adolescents. This includes prospectively evaluating and comparing the bone mineral density (BMD) change between CHB- infected adolescents 12 to < 18 years of age treated with Tenofovir DF in European treatment centers who are assigned to one of two schedules for renal and bone laboratory monitoring and BMD measurement. Primary study endpoint will be the percent changes in BMD from Baseline through study Week 96.

The secondary objectives of this study are as follows:

- To document all serious adverse drug reactions (SADR) and all renal- and bone-related adverse events (AEs), including renal and bone laboratory abnormalities
- To determine the time to diagnosis of renal and bone AEs and document the resulting patient management and outcome(s)
- To assess the clinical management and outcomes of renal- and bone-related \geq Grade 3 laboratory markers and clinical SAEs.
- To assess the efficacy and tolerability of Tenofovir DF in adolescents with CHB infection
- To assess the use of oral vitamin D, calcium and phosphate supplementation and explore the association between supplement use and rates of bone and renal AEs
- To describe the demographics and disease characteristics of adolescents with CHB infection treated with Tenofovir DF.

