3.3. Study Treatments

The proposed study is an open-label trial of 300mg oral Tenofovir DF which is equivalent to 245mg Tenofovir disoproxil, taken once daily. Tenofovir DF is packaged in white, high-density polyethylene (HDPE) bottles with a white child resistant cap. There are 30 tablets per bottle. Each bottle also contains silica gel as a desiccant to protect the product from humidity and fiber packing to protect the product during handling and shipping.

During Weeks 0 to 96, subjects will be provided with sufficient supplies for 12 weeks of dosing. At a minimum, each bottle will be labeled with a lot number, the protocol number, administration instructions, storage instructions, expiration date, Sponsor name and address. Additional information will be included according to the requirements of the protocol and local law.

Tenofovir DF will be supplied by Gilead as per its current commercial tablet formulation for the EU (300mg Tenofovir DF) for patients greater than 35 kg. There will be no difference in

medication formulation or frequency as per Tenofovir DF SmPC among subjects assigned to either Group 1 or Group 2.

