6. EFFICACY ANALYSES

6.1. Definition of the Primary Efficacy Endpoint

An efficacy analysis would be conducted after the last assigned subject completes Week 96 of TDF treatment for CHB. As the study has been prematurely discontinued, a descriptive analysis will be performed to outline the subjects who completed 96 weeks of treatment and review the HBV DNA results for subjects at their early discontinuation visit as part of study closeout proceedings.

The planned analysis will evaluate the difference in the proportion of subjects (Group 1 and 2 data will be analyzed separately and pooled as subjects have exposure to a single mode of therapy) achieving a composite endpoint of HBV DNA <400 copies/mL and ALT normal at Week 96, using a two-sided Fisher exact test with a non-completer equals excluded approach.

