6.2. Statistical Hypothesis for the Primary Efficacy Endpoint

H₀: The difference between Monitoring Groups 1 and 2 in the proportions of subjects with HBV DNA <400 copies/mL at Week 96 is equal to 0

H₁: The difference between Monitoring Groups 1 and 2 in the proportions of subjects with HBV DNA <400 copies/mL at Week 96 is not equal to 0

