6.3. Analysis of the Primary Efficacy Endpoint

The primary efficacy analysis will be conducted at the end of the study period, after the last randomized subject reaches Week 96, using the FAS. The analysis will evaluate the difference between monitoring groups in the proportion of subjects achieving the primary endpoint, using a Mantel-Haenszel test. As the study was prematurely discontinued, a descriptive analysis of subjects who met a composite endpoint of HBV DNA <400 copies/mL and ALT normal at Week 96 or at their early discontinuation visit will be reported.

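### The protocol's efficacy test has no comparator, the SAP's version compares monitoring schedules, and the two documents disagree on week, endpoint, test and missing-data rule

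*Protocol*

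**What the plan says.** Efficacy is a secondary objective: "To assess the efficacy and tolerability of Tenofovir DF in adolescents with CHB infection" (Protocol 2). All subjects receive the same drug. On formulation and dosing frequency across the two groups, Protocol 3.3 says "There will be no difference in" either.

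Protocol 8.5.1 states that "Group 1 and 2 data will be pooled, as subjects have exposure to a single mode of therapy". It then evaluates a difference in the proportion meeting a composite of HBV DNA below 400 copies/mL and "ALT normal at Week 96, using a two-sided Fisher exact test with a non-completer equals failure approach". Protocol 8.2.1.1 repeats the analysis, but with "ALT normal at Week 72, using a two-sided Fisher exact test".

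SAP 6.1 analyses the groups both separately and pooled, "using a two-sided Fisher exact test with a non-completer equals excluded approach". The null hypothesis in SAP 6.2 is that the difference between the monitoring groups "in the proportions of subjects with HBV DNA <400 copies/mL at Week 96 is equal to 0", with no ALT component. SAP 6.3 evaluates the between-group difference "in the proportion of subjects achieving the primary endpoint, using a Mantel-Haenszel test". SAP 3.9.1 makes missing = excluded (M = E) the primary approach for efficacy. SAP 6.6 lists no changes from the protocol.

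Because the study stopped early, the SAP also turns to description. SAP 2.1 says efficacy will be described. SAP 6.3 promises a descriptive report of the composite at Week 96 or at the early discontinuation visit. Table 13 in SAP Appendix 3 gives the composite by week.

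**The concern.** A test of difference needs two groups, or one group and a reference value. The protocol pools its two groups and gives neither. If the test is rescued by comparing Group 1 with Group 2, it no longer concerns the drug: a significant result would not show that tenofovir DF works, and a null result would not show that it fails. The objective calls for an estimated response proportion and its precision.

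The conflicts between sections add to this. A programmer could follow different sections to different endpoints, weeks and denominators and be able to cite the plan each time. Since SAP 6.6 reports no changes, a reader of the study report would not learn that the protocol's rule for non-completers had been reversed.

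**Working it through.** The documents give no sample size, power or effect size for efficacy, so there is no planned figure to reproduce. The power statement with the 0.10 margin (Protocol 8.9, SAP 1.4) concerns renal and bone events under the two monitoring regimens.

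**1. The specifications side by side**

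| Source | Groups | Endpoint | Timepoint | Test | Non-completers or missing |
|---|---|---|---|---|---|
| Protocol synopsis | pooled | composite | Week 96 | none named | not stated |
| Protocol 8.2.1.1 | pooled | composite | Week 72 | Fisher | failure |
| Protocol 8.5.1 | pooled | composite | Week 96 | Fisher | failure |
| SAP 6.1, planned | separate and pooled | composite | Week 96 | Fisher | excluded |
| SAP 6.1, descriptive | not stated | HBV DNA | early discontinuation visit | none | not stated |
| SAP 6.2 | Group 1 v Group 2 | HBV DNA alone | Week 96 | hypothesis only | not stated |
| SAP 6.3, planned | Group 1 v Group 2 | primary endpoint | Week 96 | Mantel-Haenszel, no stratum named | not stated |
| SAP 6.3, descriptive | not stated | composite | Week 96 or early discontinuation visit | none | not stated |
| SAP Table 13 | not in title | composite | each week to Week 96 | none | M = E |

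Within the protocol only the week conflicts. The differences in endpoint, test and missing-data rule enter with the SAP. SAP 3.9.2 adds a slip: under a heading for missing = failure, the text expands M = F as missing = excluded.

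**2. Fisher's test on pooled data.** Pooled data form one row, for example 88 responders and 12 non-responders of 100. Fisher's test conditions on the margins. With one row the margins are the data, so only one table is possible. Its probability is C(88,88) × C(12,12) / C(100,100) = 1, and p = 1 for any counts. Running it on 88/12 returned p = 1.0.

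**3. Size of the non-completer conflict.** Inputs: 30 enrolled, 15 per group (SAP 1.4); two completed 96 weeks (SAP 2.1). The exact (Clopper-Pearson) 95% limits for x of n are the 2.5% quantile of Beta(x, n − x + 1) and the 97.5% quantile of Beta(x + 1, n − x).

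- Non-completer = failure: the other 28 count as failures, so the maximum is 2/30 = 6.7%, interval 0.8% to 22.1%.
- Non-completer = excluded: the maximum is 2/2 = 100%. The lower limit is 0.025^(1/2) = 15.8%, so the interval is 15.8% to 100%.
- If one completer responds, the figures are 1/30 = 3.3% and 1/2 = 50%. If neither responds, both are 0%, with upper limits of 11.6% and 84.2%.

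**4. What a pooled estimate would show.** No response rate for the composite is given. Protocol 1.2.3.1 reports 88.5% for HBV DNA alone at Week 72 in the earlier adolescent trial. Taking that as an illustration, 0.885 × 30 rounds to 27, and 27/30 gives 73.5% to 97.9%. At an assumed 60%, 18/30 gives 40.6% to 77.3%. The intervals are wide, so precision has to be reported.

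**5. Outputs.** Table 13 spreads the composite over weeks under M = E. Listing 16 covers only HBV DNA above 400 copies/mL at the final visit. No table title in SAP Appendix 3 names the composite at Week 96 or early discontinuation that SAP 6.3 promises.

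**The case against.** The best reply is that the tests are left over from the original plan. SAP 6.1 and 6.3 both say that, because the study was stopped, a descriptive analysis will be done. SAP 2.1 describes data by group and pooled where possible, and Table 13 delivers the composite. An objective to assess efficacy on one drug can be met by description. This stands. A reader might infer from the defective tests that no stated analysis answers the efficacy objective, and the documents do not support that. SAP 6.5 on exploratory efficacy is also redacted, so nothing can be said about its content.

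Three further inferences go too far:

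- **That the SAP's Fisher test cannot be run.** Between Group 1 and Group 2 it can be computed; it just does not measure drug efficacy.
- **That Mantel-Haenszel is wrong because nothing is stratified.** SAP 3.3 rules out stratification by age or region only, and SAP 1.3 describes block assignment by site. The statistic can also be computed in a single stratum. The fair criticism is that no stratum is named.
- **That only two subjects are left for efficacy.** This holds for a strict Week 96 completer analysis. SAP 6.3 also uses early discontinuation visits, and the Week 96 window in SAP Table 3-1 runs from Day 631 to Day 714, so a subject with data in it need not have completed 96 weeks.

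What the reply does not cure: the test sentences and the hypothesis remain in the SAP beside the descriptive text. The descriptive text is itself inconsistent (HBV DNA in 6.1, the composite in 6.3). SAP 6.6 is incorrect.

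**Conclusion.** The point holds in this form. The protocol's pooled Fisher test is undefined. The SAP's between-group hypothesis and tests address monitoring schedules rather than tenofovir DF. Week, endpoint, test and missing-data rule conflict across sections, with no change recorded in SAP 6.6. A descriptive composite summary is planned, but the visible efficacy text attaches no confidence interval to it and no table title matches it.

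The two completer rules allow a Week 96 response of at most 6.7% or up to 100%. That spread assumes that all 30 enrolled subjects were dosed and so belong to the SAP's FAS, that a non-completer is anyone short of 96 weeks, and that both completers respond; it narrows if they do not. It describes the rules as written, not the Week 96 or early discontinuation summary in SAP 6.3, where more subjects contribute. Efficacy is secondary and the final analysis is largely descriptive, so this should be corrected but does not undermine the study's main purpose.

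**What to change.** Make the change in the SAP. SAP 2.1 dates the last patient's last visit to April 2018, so a protocol amendment would alter no conduct.

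1. Delete the hypothesis in 6.2 and the Fisher and Mantel-Haenszel sentences in 6.1 and 6.3.
2. Name one efficacy estimate: the pooled proportion of the FAS with HBV DNA < 400 copies/mL and normal ALT at Week 96 or the early discontinuation visit, with an exact 95% CI. Show proportions by monitoring group without a test, and align the descriptive text of 6.1 with this.
3. State one denominator and one missing-data rule for it, for example all FAS subjects with missing = failure, and M = E as sensitivity. Correct the wording of 3.9.2.
4. Add a table to Appendix 3 with that title. Early discontinuation visits fall at different treatment durations, so label the result accordingly.
5. In 6.6, record the changes from the protocol: test dropped, missing-data rule, use of the early discontinuation visit. Also record that Week 96 is the timepoint, not the Week 72 in Protocol 8.2.1.1.

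The cost is SAP wording and one table, with less testing to program than is now written.

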8.5.2. Secondary Analyses

Not applicable

8.6. Safety Analysis

All safety data collected on or after the date that Tenofovir DF was first dispensed up to the date of last dose of Tenofovir DF will be summarized by monitoring group. Data for any pre-treatment and treatment-free follow up periods will be included in data listings.

The primary safety analysis will be performed after the last assigned subject reaches Week 96. The analysis will evaluate the difference between renal or bone AEs recorded within each of the monitoring groups with respect to the primary safety endpoint, estimating the cumulative incidence proportions using time-to-event methodology and performing comparisons using 95% confidence intervals for differences in proportions.

The proportion of subjects in each monitoring group with renal or bone AE leading to permanent discontinuation of Tenofovir DF through Week 96 will be summarized. Descriptive statistics such as n, mean, standard deviation, median, Q1, Q3, minimum and maximum) by monitoring group will be used to report demographics and time to event summaries, and a Wilcoxon rank sum test may be used to compare AEs between monitoring groups.

For categorical safety data including incidence of AEs and categorizations of laboratory data, a Fisher's exact test will be used to compare monitoring groups. For continuous safety data including laboratory data, a Wilcoxon Rank sum test will be used to compare monitoring groups. Subgroup analyses of safety endpoints will include analyses by assigned monitoring group, age groups, and geographical location of study site.

8.6.1. Extent of Exposure

A subject's extent of exposure to drug treatment will be generated from the Tenofovir DF drug administration page of the CRF. Exposure data will be summarized by monitoring group.

8.6.2. Adverse Events

Clinical and laboratory AEs will be coded using the Medical Dictionary for Regulatory Activities (MedDRA). System Organ Class (SOC), High-Level Group Term (HLGT), High-Level Term (HLT), Preferred Term (PT), and Lower-Level Term (LLT) will be attached to the clinical database.

Events will be summarized on the basis of the date of onset for the event. A treatment-emergent adverse event will be defined as any adverse event that begins on or after the date of first dose up to the date of last dose of Tenofovir DF plus 30 days.

Summaries (number and percentage of subjects) of treatment-emergent AEs related to **bone or renal SOCs** (hierarchically ordered by SOC, HLT, and PT) will be provided by treatment group:

- all treatment-emergent bone or renal AEs,
- all related treatment-emergent bone or renal AEs,
- combined Grade 2, 3, and 4 treatment-emergent bone or renal AEs,
- combined Grade 3 and 4 treatment-emergent bone or renal AEs,
- combined Grade 2, 3, and 4 related treatment-emergent bone or renal AEs,
- combined Grade 3 and 4 related treatment-emergent bone or renal AEs,
- all AEs that caused permanent discontinuation from Tenofovir DF,
- all AEs that caused permanent discontinuation from study,
- all AEs that caused change in dose or temporary interruption of Tenofovir DF,
- all serious AEs (all SOCs, i.e., not limited to bone or renal SOCs), and
- all serious bone or renal related AEs.

Events will be summarized based on the date of onset for the event. A treatment-emergent adverse event will be defined as any adverse event that begins on or after the date of first dose of Tenofovir DF. Events that occur prior to the first dose of Tenofovir DF or after the last dose of Tenofovir DF will be included in data listings.

PPD

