300mg oral Tenofovir disoproxil fumarate (Tenofovir DF), which is equivalent to 245mg Tenofovir disoproxil, following enhanced patient monitoring protocol for bone and renal biomarkers

Reference Therapy,
Dose, and Mode of
Administration:

300mg oral Tenofovir DF following local standards of care for patient monitoring for renal biomarkers

Criteria for Evaluation:

Safety:

The primary safety endpoint is the indication of a cumulative incidence of a $\geq 4\%$ decrease from Baseline BMD of the spine or whole body through Week 96. Secondary endpoints include bone and renal AEs. Bone AEs may include reports of bone pain or fractures. Renal AEs may include reductions in creatinine clearance, and clinical and laboratory evidence of Grade 3 or greater renal tubulopathy or toxicity (e.g. proximal renal tubulopathy, Fanconi syndrome).

Bone and renal AEs, concomitant medications (including dietary supplements) and specified clinical laboratory tests will be collected each time subjects from Group 1 or Group 2 return for scheduled monitoring by the study site over a 96 week period.

Efficacy:

An efficacy analysis will be conducted after the last assigned subject reaches Week 96. The analysis will evaluate the difference in the proportion of subjects (Group 1 and 2 data will be pooled, as subjects have exposure to a single mode of therapy) achieving a composite endpoint of HBV DNA < 400 copies/mL and ALT normal at Week 96.

Pharmacokinetics: Not applicable

Statistical Methods:

The primary safety analysis will be performed after the last subject reaches Week 96 on Tenofovir DF treatment among both monitoring groups. The primary analysis will evaluate quantitative reductions in spine or whole body BMD compared to baseline assessments through DEXA scanning. A key secondary study objective is to assess within-group and between-group differences in renal biomarker changes (e.g., creatinine clearance using the Schwartz formula, glucosuria, proteinuria) suggestive of renal toxicity. To evaluate the time to detection of renal or bone AEs among the assigned monitoring groups, estimations of incidence rates (events over person time on Tenofovir DF) and time to event analysis will be determined. The evaluation of other clinically relevant endpoints such as sustained virologic response, serologic status, and development of Tenofovir DF resistance will also be assessed as secondary study outcomes for each monitoring group and as a combined cohort.

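### The protocol gives incompatible end points for summarising safety events. The SAP's + 30 days settles only the treatment-emergent AE count, leaving + 7-day rules and an ambiguous person-time stop.

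*Protocol*

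**What the plan says.** **Event window, protocol.**
- Section 8.6 summarises safety data from first dispensing "up to the date of last dose of Tenofovir DF will be summarized by monitoring group" and sends treatment-free follow-up to listings.
- Section 8.6.2 gives two definitions of a treatment-emergent event. The first covers an event that "begins on or after the date of first dose up to the date of last dose of Tenofovir DF plus 30 days". The second is: "A treatment-emergent adverse event will be defined as any adverse event that begins on or after the date of first dose of Tenofovir DF". It has no end date. The next sentence reads: "Events that occur prior to the first dose of Tenofovir DF or after the last dose of Tenofovir DF will be included in data listings".
- Section 8.2.1.1, under the efficacy heading, states: "All data collected during the course of the study (on treatment and during the treatment-free follow up window) will be included in the safety summaries".
- Section 8.2.1.2 uses treatment plus 30 days. Section 8.6.3 makes laboratory abnormalities listing items only after last dose + 30 days.

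**Event window, SAP.** Sections 2.1 and 7.1.5.1 use last dose + 30 days. Section 7.1.5.2 classifies incomplete onset dates by the month and year of the 7th day after last dose. Section 7.2 cuts laboratory tables for early stoppers at last dose + 7 days, while 7.2.2.1 and 7.2.2.2 run to + 30 days. Section 7.8 reports no alteration to the protocol's safety analysis.

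**Person-time.** The protocol synopsis plans "estimations of incidence rates (events over person time on Tenofovir DF". Sections 3.1 and 8.1.3 say that event-free subjects "will contribute cumulative exposure time on Tenofovir DF from Baseline to Week 96 or to study discontinuation". Section 6.5 keeps subjects who stop drug in the study where possible, and 3.2 follows them off treatment for 24 weeks or until other treatment starts. Section 7.3 collects bone and renal AEs to 30 days after last dose.

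**The concern.** Whether an event found shortly after stopping drug enters a summary table depends on which section the programmer follows. The same applies to the time a subject contributes to a rate. If events and person-time are cut at different dates, the incidence rate is biased even when each cut is reasonable alone. The rate is a stated secondary endpoint (8.1.3). Section 8.6.4 also compares the decrease of at least 4% in BMD by person-time rates. With only 4-5 bone or renal drug reactions expected in the planned 100 subjects (8.9), and 30 enrolled, reclassifying one event would be visible.

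**Working it through.** The plan states no figure to reproduce here. The check is a comparison of texts, then arithmetic for size.

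**1. Two test cases for the event window.**

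| Rule | Onset day 10 after last dose | Onset day 60 after last dose |
|---|---|---|
| Protocol 8.6 | listed | listed |
| 8.6.2, first definition | summarised | not treatment-emergent |
| 8.6.2, second definition | treatment-emergent | treatment-emergent |
| 8.6.2, last sentence | listed | listed |
| 8.2.1.1 | summarised | summarised |
| 8.2.1.2 | summarised | outside |
| SAP 2.1 and 7.1.5.1 | summarised | outside |

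The protocol rules agree on neither case. Under 7.3, a non-serious bone or renal AE on day 60 is not due for collection. For those events the live conflict is last dose against + 30 days; the longer window can add only SAEs and laboratory or DEXA data.

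**2. The SAP's 7-day rules.** Take an invented last dose of 20 March. The 7th day after is 27 March and the 30th is 19 April. An event dated 5 April is treatment-emergent under 7.1.5.1. The same event recorded only as April is not under 7.1.5.2, because April is later than the month of the 7th day. A laboratory value on day 20 after last dose in an early stopper is outside the tables under 7.2 but can be a treatment-emergent abnormality under 7.2.2.1.

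**3. Size of a mismatch between events and person-time.** Let E be weeks on drug, with a constant hazard; 30 days = 30/7 = 4.29 weeks. E = 96 is the planned duration; 72, 48 and 24 are assumptions, because the documents give no mean exposure.
- A: events to + 30 days over on-drug time, ratio to the true rate (E + 4.29)/E.
- B: events to last dose over on-drug time plus a full 24 weeks off drug, E/(E + 24).
- C: as B, but events counted to + 30 days, (E + 4.29)/(E + 24).

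| E (weeks) | A | B | C |
|---|---|---|---|
| 96 | 1.045 | 0.80 | 0.84 |
| 72 | 1.06 | 0.75 | 0.79 |
| 48 | 1.09 | 0.67 | 0.73 |
| 24 | 1.18 | 0.50 | 0.59 |

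A overstates by 4.5% at 96 weeks and by 6-18% at 72-24 weeks. B understates by 20% and by 25-50%. B and C are limits: they need a full 24 weeks of follow-up and a literal reading of study discontinuation. At E = 96 they also need that date to override the Week 96 stop in the same sentence, so the 20% is the least likely to arise.

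**4. In rate units.** Five events in 100 subjects treated for 96 weeks (672 days) give 100 × 5/(100 × 672/365.25) = 2.72 per 100 person-years on drug. With person-time to + 30 days (702 days) the rate is 2.60.

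**The case against.** The SAP fixes the treatment-emergent AE window at + 30 days for the final analysis. The protocol itself contains that window, so for this count the no-alteration statement is defensible. Both person-time wordings say on Tenofovir DF, and SAP 4.3.1 measures exposure from first to last dose. No visible SAP table reports a person-time rate, and SAP 7.1.7 is redacted, so a rate definition may exist there. The last visit was in April 2018, so only the SAP or the report can still change. All of this stands. It narrows the point to conflicting protocol text, the SAP's 7-day rules, and a denominator not settled in any visible text.

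A reader might infer more than the documents support:
- **That off-treatment follow-up inflates bone and renal AE rates by 33-100%.** That is (E + 24)/E at 72 and 24 weeks. It needs AEs collected over the full 24 weeks, but 7.3 stops non-serious bone and renal AEs at + 30 days.
- **That nearly all subjects are affected.** Only two patients completed 96 weeks, but the study was closed early. The documents do not say how many entered off-treatment follow-up, and at closure last dose and study exit may nearly coincide.
- **That the person-time definitions flatly contradict each other.** They share the on-drug wording; what is unclear is where the time stops.
- **That 8.6.2 sends late events to listings only.** It does not say only. The conflict between 8.6 and 8.2.1.1 does not depend on that word.

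**Conclusion.** The inconsistency is real and should be corrected, but its reach is limited. Protocol 8.6.2 carries two definitions with different ends, and 8.6 and 8.2.1.1 treat off-treatment data in opposite ways. The SAP resolves the treatment-emergent AE count without recording that it chose among conflicting rules, and adds 7-day cuts that disagree with its own 30-day rule. Person-time has an ambiguous stopping point.

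AE counts move only if events fall after last dose or, under the SAP, if their onset dates are incomplete. If a rate is reported, the likeliest mismatch is the small one (A in the working). The understatement in B is an upper bound. All sizes assume a constant hazard, which is doubtful after stopping, since protocol 1.4 describes renal injury as reversible on discontinuation.

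**What to change.** Use first dose to last dose + 30 days for both AE counts and person-time, for completers and early stoppers alike, censoring at end of observation if earlier.

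- **Protocol wording:** apply this in the synopsis, 3.1, 8.1.3, 8.2.1.1, 8.6 and 8.6.2, and delete the second treatment-emergent definition with its last-dose listing cut. Replacing study discontinuation alone is not enough: completers' time would still end at Week 96 while their events count to + 30 days, and the synopsis would still divide by time on drug.
- **SAP:** in 7.1.5.2 replace the 7th day by the 30th. Reconcile the + 7-day cut in 7.2 with 7.2.2.1, either by using 30 days in both or by stating which tables each cut governs. Define the rate denominator. Keep 4.3.1 as the description of exposure.
- **Reporting:** show later off-treatment events in a separate row and record the choice in SAP 7.8.

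The window matches AE collection in 7.3 and the 30-day follow-up assessment in Appendix 2. The cost is wording and a small programming change. No new data are needed; a few incompletely dated events or late laboratory values may move between tables. With the study closed, the change belongs in the SAP and the study report.
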